9.4.2 Method of implementing the allocation

Participants not removed from the study due to non-adherence or significant allergy or intolerance to the glucose sensor will be randomised during visit 3 using the web-based randomisation platform

SealedEnvelope.com. The responsibility for randomising participants into the trial lies with the Principal Investigator and staff at sites. Access to the randomisation system will be limited to the core study team members at each trial site. The delegation log at each trial site should clearly identify which roles and/or individuals are delegated to perform the randomisation procedure on the SealedEnvelope.com web platform. Individuals undertaking the randomisation will be required to enter the patient's initials, month/year of birth, date of randomisation, site and confirmation of eligibility criteria into the SealedEnvelope.com secure website, before being permitted to randomised participants. The system will need to record the unique trial ID which will be assigned to each participant during screening (Visit 1) and should be used on all trial documentation (CRF, SAE forms etc.). This ID will be sequential across all NHS sites and will consist of a three digit site reference followed by the sequential across site ID. Following randomisation an email confirmation with the allocated randomised treatment and trial ID will be disseminated to the trial site staff and key CTU personnel, automatically via the randomisation system. A copy of this confirmation should be filed in the participant's study notes. An emergency contact card should be pre-populated with the trial ID. Further details of the randomisation process will be provided in a user manual.

9.4.3 Initiation of study treatment

Body weight measurement will be made where possible. Participants will be provided with necessary training on use of study devices according to randomisation. Participants will also be provided with a paper diary to collect information about insulin doses and carbohydrate intake in last 5 days before study visits 4, 5 and 7 (Appendix 13).

9.4.4 Training session (Appendix 9)

Participants randomised to the flash-glucose monitoring arm will receive education and training about insertion and initiation of the sensor as well as how to use flash-glucose monitoring data for treatment optimisation. They will be encouraged to download data at home to identify pattern recognition. This session will be conducted by a professional diabetes educator or a member of the study team. Education will be tailored to meet the needs of the individual.

Participants randomised to conventional finger-stick glucose monitoring arm will be encouraged to use finger-stick glucose levels to optimise treatment and will receive education about insulin dose adjustments using finger-stick glucose levels. The study will try to mimic real-life conditions by continuing participant's pre-study diabetes treatment unchanged and finger-stick glucose testing frequency as determined by the participant as required. Participants in both arms will also receive training on sick day rules and dealing with hypo and hyperglycaemia.

Participants assigned to either arm will receive an information leaflet following the training session. The information provided will be tailored to suit the trial arm for which they will be assigned to. The leaflet provided to those who will be randomised to the Flash Glucose Monitoring arm will include sign-posting to educational videos provided by the Association of British Clinical Diabetologists (ABCD) (<https://abcd.care/dtn/education>) and Bertie online (www.bertieonline.org.uk) for those in the blood glucose monitoring arm .

9.5 Visit 4: (+4 weeks since randomisation): Review data and treatment optimisation

Purpose of this visit is to review data from Flash-glucose monitoring and finger-stick glucose monitoring to further optimise treatment. Study devices will be downloaded. Information about insulin doses and any adverse events will be collected.

9.6 Visit 5: (+12 weeks since randomisation): Review data and treatment optimisation

Purpose of this visit is to review data from Flash-glucose monitoring and finger-stick glucose monitoring to further optimise treatment. Study devices will be downloaded. Information about insulin doses, participant diaries and any adverse events will be collected. Blood sample will be collected for HbA1c.

9.7 Visit 6: (+22 weeks since randomisation): Finger-stick glucose monitoring arm only

Participants randomised to finger-stick glucose monitoring arm will have an extra visit 10 weeks after visit 5 to insert a blinded glucose sensor for data capture. Participants who join the trial by virtual consultation will receive a Blinded FSL2 pro sensor and reader by post for self-insertion with relevant advice. At the end of the two weeks the participant can return the items to the research team by pre-paid postal services.

9.8 Visit 7: (+24 weeks since randomisation): End of randomised study treatment

The participant will be invited to attend the research centre approximately 12 weeks after Visit 5. This would be the end of 24 weeks randomised study period. All study devices will be downloaded.

Insulin usage data will be recorded and diaries collected. The participant will have a blood test for the HbA1c. Body weight measurement will be made where possible. Participant will be asked to complete questionnaires evaluating diabetes related quality of life, diabetes distress and diabetes treatment satisfaction. In addition, participants in the FSL2 arm will be asked to complete a questionnaire exploring expectations and experience of using FSL2 during the study. For those participants who have completed the trial by virtual means, any remaining devices, completed study documents and blood collections for HbA1c testing can be returned free of charge with pre-paid return postage.

9.9 Participant Withdrawal Criteria

The following pre-randomisation withdrawal criteria will apply:

1. Participant is unable to demonstrate safe use of flash-glucose monitoring during run-in period as judged by the investigator
2. Participant develops significant allergy to sensor plaster

The following pre- and post-randomisation withdrawal criteria will apply:

3. Participant may terminate participation in the study at any time without necessarily giving a reason and without any personal disadvantage
4. Significant protocol violation or non-adherence
5. Decision by the investigator or the sponsor that termination is in the Participant's best medical interest
6. Participant becomes pregnant during the study period
7. Allergic reaction to insulin
8. Allergic reaction to glucose sensor
9. If patient cannot be contacted over a period of 4 weeks then the participant will be considered lost to follow up

Participants who are withdrawn for reasons stated in (4), (5), (7), and (8) may be invited to provide the blood sample for the assessment of HbA1c and complete the self-report questionnaires at the end of the planned study intervention period.

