14.2 Statistical Analysis Plan (SAP)

All analyses will be conducted following the intention to treat (ITT) principle where all randomised participants are analysed in their allocated treatment group whether or not they receive their randomised treatment. All baseline, 12-week and 24-week outcome data will be presented descriptively, both overall and within treatment group, using mean (SD), median (IQR) or frequency (percentage), as appropriate. All statistical tests will use a 2-sided significance level of 5% (unless otherwise specified). All confidence intervals presented will be 95% and two sided.

A full, detailed SAP will be approved by the TSC (following drafting and review by the TMG, TSC and IDMC) before the first substantive statistical analysis. All statistical analyses will be performed using Stata (StataCorp, College Station TX, USA).

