#### **3.3 Analysis populations**

All efficacy and safety analyses will be conducted following the ITT principle where all randomised participants are analysed in their allocated treatment group whether or not they receive their randomised treatment according to the protocol.

The primary outcome analysis will be conducted based on a complete-case analysis approach unless there is more than 10% of participants who have missing HbA1c at 24 weeks (or more than a 10% difference between missing data percentages in the two arms), in which case multiple imputation will be used in order to implement a more complete ITT analysis of the substantive Analysis of Covariance (ANCOVA) model (otherwise this will be performed as a sensitivity analysis, with a complete case analysis used as the primary analysis).

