#### **5.2.3 Sensitivity analyses**

Sensitivity analyses will examine robustness of the primary outcome results to assumptions regarding missing data by performing multiple imputation (see Section 5.3).

The primary outcome analysis will also be repeated having included additional covariates for the consideration of improved precision. These covariates will include age, sex, BMI duration of diabetes, deprivation index quintile.

Complier-Adjusted Causal Effect (CACE) will be used, implemented using an instrumental variables approach, to estimate the causal effect of the FSL device glucose monitoring relative to finger-stick glucose monitoring. Appropriate definitions of non-compliance (adherence) will be investigated within this sensitivity analysis, including the simple definition in the finger-stick monitoring arm of non-compliance equating to use of FSL device glucose monitoring for at least 10 days between the 3-month and 6-month outcome assessment.

Additional sensitivity analyses will be conducted to assess the impact of primary outcome data collected outside the visit window as specified in the protocol, that is:

- +/- 2 weeks of the planned visit date or
- +/- 4 weeks of the planned visit date.

Further sensitivity analyses will be performed to assess the potential impact of COVID-19 on the primary outcome. These will include the exclusion of participants whose treatment or outcome assessment was deemed severely impacted by COVID-19.

Finally, additional sensitivity analyses will be introduced to examine for the impact of protocol deviations or other unexpected events that may not have been captured in the protocol, including the impact on key secondary outcomes, where deemed necessary.

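### Protocol 9.9 leaves the 24-week HbA1c to site discretion after withdrawal for non-adherence or sensor allergy, which puts the promised intention-to-treat analysis at risk

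*Protocol*

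**What the plan says.** Protocol 9.9 lists reasons (3) to (9) as applying after randomisation. Reason (4) is "Significant protocol violation or non-adherence" and reason (8) is "Allergic reaction to glucose sensor". On outcome collection it says: "Participants who are withdrawn for reasons stated in (4), (5), (7), and (8) may be invited to provide the blood sample", together with the questionnaires, at the end of the planned intervention period. Reasons (3), (6) and (9) are not on that list. Reason (9) reads: "If patient cannot be contacted over a period of 4 weeks then the participant will be considered lost to follow up".

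Protocol 14.2 commits to an intention-to-treat analysis in which "all randomised participants are analysed in their allocated treatment group whether or not they receive their randomised treatment"; SAP 3.3 repeats this for efficacy and safety. Under SAP 3.3 the primary analysis is complete case "unless there is more than 10% of participants who have missing HbA1c at 24 weeks", or unless the missing percentages in the two arms differ by more than 10%. In either of those cases multiple imputation becomes primary. SAP 5.2.3 states: "Sensitivity analyses will examine robustness of the primary outcome results to assumptions regarding missing data by performing multiple imputation". SAP 5.3 puts baseline and 12-week HbA1c in the imputation model. SAP 5.2.3 also plans a complier analysis, of which it says: "Appropriate definitions of non-compliance (adherence) will be investigated within this sensitivity analysis".

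**The concern.** An intention-to-treat estimate needs the 24-week HbA1c from people who stopped the device as well as from those who kept using it. Section 9.9 does not require sites to seek it from the people most likely to have stopped. Nothing in the text available separates stopping the device from leaving follow-up.

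The loss is unlikely to be even between arms. After randomisation FSL2 participants wear sensors for 24 weeks, while controls wear one only for the last two (Protocol 9.7), so reason (8) falls mainly on FSL2. How reason (4) divides between arms is unknown. The trial is open-label, so knowledge of allocation can affect who leaves and whom a site chooses to invite.

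If the unmeasured FSL2 participants are those who stopped the device, both complete case and imputation tend to overstate the effect of offering it. The complier analysis has the same dependence, since it needs outcomes from non-adherers. The HbA1c result also feeds the long-term economic model (Protocol 14.3).

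**Working it through.** **Inputs.** From Protocol 14.1: 150 randomised 1:1 (75 per arm), 128 evaluable, difference 0.4, SD 0.8. From SAP 3.3: the two 10% triggers. From Protocol 4.3 and 4.7: 7 device-related withdrawals among 328 participants in the large European trial of the earlier device. The withdrawal fractions, outcomes after withdrawal and 12- to 24-week correlation used below are assumptions.

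**1. The plan's own figure.** The standard error is 0.8 × √(2/64) = 0.141. A two-sided 5% t-test with 64 per arm has power 0.80, as stated, and 150 × 0.85 = 127.5, in line with 128. The sample size is not in question. Measuring all 150 would raise power at most from 0.80 to 0.86 (baseline correlation 0), or from 0.90 to 0.94 (correlation 0.5). The main issue is bias.

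**2. How uneven can losses be with complete case still primary?** The arm difference must not exceed 10 points: 7/75 = 9.3 passes and 8/75 = 10.7 does not, so the largest excess is 7. Total missing must not exceed 15 of 150. With c lost in control and c + 7 in FSL2, 2c + 7 ≤ 15 gives c = 4. So 11/75 (14.7%) against 4/75 (5.3%), 10.0% overall, leaves complete case primary.

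**3. Benchmark rate.** 7/328 = 2.1%. If all seven were device users in one of two equal arms (assumed), 7/164 = 4.3%, and 0.043 × 75 = 3.2, about 3 participants here.

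**4. Lost benefit.** Let a fraction w of the FSL2 arm be removed unmeasured and gain nothing, while the rest gain d = 0.40. The true effect in all randomised is (1 − w)d, complete case estimates d, and the overstatement is w × d.

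| w | True effect | Complete case | Overstatement |
|---|---|---|---|
| 0.04 | 0.384 | 0.400 | 0.016 (4.2%) |
| 0.08 | 0.368 | 0.400 | 0.032 (8.7%) |
| 7/75 | 0.363 | 0.400 | 0.037 (10.3%) |

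The last row treats 7 of the 11 FSL2 losses in step 2 as device-related, above a background of 4 that matches control. If all 11 gained nothing, the figure is 11/75 × 0.40 = 0.059.

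**5. Worse prognosis.** If those removed would also have ended g = 0.3 above their arm's average (assumed), add w × g/(1 − w): 0.04 × 0.3/0.96 = 0.013, or 0.08 × 0.3/0.92 = 0.026. Similar losses in control would offset this part.

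**6. Does imputation repair it?** This was simulated with 1,000,000 per arm, SD 0.8, baseline to follow-up correlation 0.5, 12- to 24-week correlation 0.7 (assumed) and trial arm in the imputation model. At w = 0.08:

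- complete-case bias: 0.032
- imputed, withdrawal before week 12 so no 12-week value: 0.032
- imputed, 12-week value still shows full benefit: 0.032
- imputed, 12-week value already shows no benefit: 0.013

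The last result can be checked by hand. The slope of 24-week on 12-week HbA1c given baseline is (0.7 − 0.5 × 0.5)/(1 − 0.5²) = 0.6, so 60% of 0.032 is recovered and 0.4 × 0.032 = 0.013 remains.

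**The case against.** The strongest reply is that the effect is small and every size rests on assumption. The case closest to the documents is about 3 of 75 participants and 0.016 points, or 11% of the planning standard error (0.016/0.141). The benchmark comes from an earlier device, whose design was later changed to be kinder to skin (Protocol 4.7). Adhesive allergy is an exclusion, and the run-in removes people who react to the sensor or wear it for fewer than 10 of 14 days. Controls may leave too. All of this stands, and it is why the size is called small.

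The plan also has real safeguards: a 15% attrition allowance, imputation using 12-week HbA1c and predictors of missingness, and room in SAP 5.2.3 for further sensitivity analyses of protocol deviations. These help but do not close the gap. Step 6 shows when imputation recovers nothing, and the further analyses are discretionary, with none named that departs from missing at random.

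It is also fair that nobody can be compelled under (3), and that someone lost under (9) may be unreachable. Participant information and consent text was not available and may say more. The request for these two reasons is therefore only to ask, or to attempt. Finally, planning a complier analysis suggests that many non-adherers are expected to stay in follow-up; section 9.9 should then say so.

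**Conclusion.** The concern holds and should be fixed. Section 9.9 makes the primary outcome optional for people whose data the intention-to-treat analysis needs, and it is silent for (3) and (9). Pregnancy (6) is in the same position. Intention to treat is not replaced, but it depends on outcomes that sites need not seek.

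The bias is probably small: 0.016 to 0.037 points on a planned effect of 0.40, under the assumption that removed FSL2 participants gain nothing and the rest gain 0.40. A worse prognosis among them would add to this, and similar control losses would offset that addition. The documents give neither the withdrawal rate nor the outcomes after withdrawal in this trial, so these are scenarios and not estimates. Confidence is high on the text and the direction of risk, and limited on the size.

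**What to change.** Leave every rule on stopping the device and on withdrawal as it stands, and change only data collection and analysis.

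- **Protocol 9.9, reasons (4), (5), (7), (8):** replace the optional invitation with a statement that participants will be asked for the 12-week HbA1c (if not yet reached), the 24-week HbA1c and the end-of-period questionnaires. Use the testing route the participant already used, as section 12.3.1 requires.
- **Reason (3):** ask unless consent to follow-up is also withdrawn. **Reason (9):** attempt the 24-week HbA1c before recording it as missing. State what is sought under (6).
- **SAP 5.2.3:** add a delta-adjusted (missing-not-at-random) analysis, for example raising imputed FSL2 values by 0 to 0.4 points, where 0.4 equals loss of the whole planned benefit. Report the shift at which the conclusion changes.
- **Reporting:** give withdrawals by reason and arm, with the number who still provided HbA1c, alongside the CONSORT diagram already planned.

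The cost is one protocol wording amendment (with ethics committee and sponsor approval under section 20 if substantial), a short SAP addition, some postal kits and a few extra contacts. The 12-week sample is a new request of people who have already been withdrawn.

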9.10 Study Stopping Criteria

The study may be stopped if three consecutive participants withdraw on safety grounds or on the advice of an Independent Data Monitoring Committee (IDMC)

9.11 End of Trial

For regulatory purposes, the end of trial will occur at each study site when the last participant has undergone their final assessment and the data has been collected. The declaration of end of trial form will be submitted to regulatory authorities. The Manchester CTU will notify the REC and the HRA at the end of a clinical trial (when all participating sites have completed final participant assessments) within 90 days of its completion. Following this, Manchester CTU will advise sites on the process for closing the trial at site.

9.12 Support telephone line

There will be a telephone helpline to the local research teams for participants in case of any technical device or problems related to diabetes management such as hypo- or hyperglycaemia during normal working hours. Outside working hours participants will be advised to contact usual out hours NHS support services.

9.13 Participant reimbursement

The study will provide the FSL2 device and related consumables. Participant will continue their usual glucose meter, and glucose test strips. Reasonable travel expenses will also be reimbursed for those who adopt face-to-face clinic visits. No participant reimbursement will be provided to those who opt for virtual (at-home) visits. After completing the study, participants will not keep the study devices. They will revert to their conventional finger-stick glucose monitoring.

10 Endpoints

10.1 Primary Endpoint

The primary outcome (endpoint) is HbA1c at 24 weeks.

10.2 Secondary Endpoints

10.2.1 *HbA1c based*

- HbA1c at 12 weeks
- HbA1c \leq 53 mmol/mol (7.0%)
 - at 12 weeks [yes/no]
 - at 24 weeks [yes/no]
- HbA1c \leq 59 mmol/mol (7.5%)
 - at 12 weeks [yes/no]
 - at 24 weeks [yes/no]
- Reduction in HbA1c \geq 5.5 mmol/mol (0.5%) from baseline (screening)
 - at 12 weeks [yes/no]
 - at 24 weeks [yes/no]
- Reduction in HbA1c \geq 11 mmol/mol (1.0%) from baseline (screening)
 - at 12 weeks [yes/no]
 - at 24 weeks [yes/no]

10.2.2 *Sensor based:*

- Time spent in the target glucose range between 3.9 to 10.0 mmol/l (70 to 180mg/dl).
- Time spent below target glucose (<3.9mmol/l) (<70mg/dl)
- Time spent above target glucose (10.0 mmol/l) (180 mg/dl)
- Average glucose levels
- Standard deviation glucose levels
- Coefficient of variation glucose levels
- The time with sensor glucose levels:
 - < 3.5 mmol/l (63 mg/dl)
 - < 3.0 mmol/l (54mg/dl)
 - < 2.8 mmol/l (50 mg/dl)

- The time with sensor glucose levels in the significant hyperglycaemia (glucose levels > 16.7 mmol/l) (300mg/dl)
- AUC of glucose below 3.0mmol/l (54mg/dl)

All the sensor based metrics will also be analysed separately for daytime (7:00-23:00 hours) and night-time (23:00-7:00 hours) in addition to overall period.

10.2.3 Non-sensor based secondary clinical:

- Daily average total insulin dose
- Daily average basal insulin dose
- Daily average bolus dose
- Average number of boluses of rapid acting insulin per day
- Frequency of severe hypoglycaemic episodes as defined by American Diabetes Association
- Frequency of significant ketosis events (plasma ketones >3mmol/l)
- Nature and severity of other adverse events.

10.2.4 Non-sensor based secondary patient-reported (psychosocial):

- Type 1 Diabetes Distress Scale (T1-DDS)
- Quality of Life (EQ-5D-5L)
- Patient Health Questionnaire (PHQ-9)
- Diabetes fear of injecting and self-testing questionnaire (D-FISQ)
- The revised Diabetes Eating Problem Survey (DEPS-R)

10.2.5 Process evaluation (utility and acceptability)

- FSL2 device utilization data, including: average number of scans per day (7:00-23:00 hours), per night (23:00-7:00 hours) and over the full 24-hour period; average number of days of usage per week
- Number of finger-stick glucose level tests per day
- Diabetes Treatment Satisfaction Questionnaire (DTSQ)
- Glucose Monitoring Satisfaction Survey (GMSS)

11 Assessment and Reporting of Adverse Events

11.1 Definitions

11.1.1 Reportable Adverse Events

A reportable Adverse Event is any untoward medical occurrence that meets criteria for a serious adverse event or any unanticipated medical occurrence in a study participant that is study or device-related. Device deficiencies that could have led to a serious adverse device effect will also be reported.

